11.0 ENDPOINTS AND STATISTICAL ANALYSIS PLAN**11.1 Endpoints Analyses and Reporting of Results**

The study objective is to assess the safety and performance of the PQ Bypass Stent Graft System to access, deliver guidewires and implant stent grafts. The statistical methods for the primary endpoints are pre specified in this analysis plan and cannot be changed at the time of analysis.

All subjects will be followed on an intent to treat basis. The device performance will be assessed based on a per protocol analysis of the primary safety and effectiveness endpoints. An Intent to treat analysis, along with other secondary analyses, will also be completed and reported. Demographic, baseline clinical and disease characteristics, procedural results and primary, secondary and all additional endpoints will be summarized using descriptive statistics. All statistical analyses will be performed using SAS for Windows version 9.1 or higher.

As noted above, up to 65 subjects with a documented untreated, atherosclerotic lesions of the native superficial femoral artery (SFA) or the superficial femoral and proximal popliteal arteries, suitable for treatment with PQ Bypass Stent Graft may be enrolled in the study to ensure an appropriate sample size of 60 evaluable subjects post treatment.

- Safety assessment will be achieved by recording and measuring Major Complication rates/Serious Adverse Event rates associated with the PQ Bypass stent grafts. The primary safety endpoint (MAE) and MAVE will be presented using descriptive statistics at various time intervals. Using the Wilson Method, the one sided upper 95% confidence bound will be calculated and presented.
- The primary performance hypothesis will be tested by calculating the one sided 95% lower confidence limit for the rate of successful performance using the Wilson Method. If the lower limit exceeds the performance goal rate of 70% the null hypothesis will be rejected and the endpoint will be met. In addition to hypothesis testing, descriptive statistics of the primary performance endpoint will include the total number and percentage of patent PQB grafts.
- Descriptive statistics of the primary performance endpoint which includes total number of patent PQ Bypass grafts, percentage of patent PQ Bypass grafts, and the one sided 95% CI of the percentage using the Score approximation will be presented. The lower bound of the one sided 95% CI will be will be calculated and presented.

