- The secondary endpoint of primary assisted and secondary patency will be summarized using Kaplan Meier survival analysis. Life tables will be created and a Kaplan Meier survival curve will be presented.
- Other secondary endpoints will be summarized by providing point estimates,

number of subjects, and 95% confidence bounds calculated using the Score approximation.

The primary patency rate of the PQ Bypass Stent Graft is expected to be superior to a historical control rate due to its design in lesion lengths 8 18 TASC B C lesions.

In order to establish a historical control rate, a literature review was performed on reported patency outcomes for percutaneous treatment of lesions between 8 18 centimeters in length corresponding to TASC II B and C Lesions Results are illustrated in **Figure 8** and **Figure 9** below. References on file at PQ Bypass.

Figure 8: Reported Patency Rates Across TASC II Class A-D Modalities Over Time

[figure not shown]
[figure not shown]

Figure 9: SFA and Popliteal Endovascular Therapies 12-month Primary Patency

References on file

In order to establish a statistical sample size, a delta of 10%, and a one sided α of 0.05 were set to demonstrate superiority of the PQ Bypass Stent Graft relative to the historical control in terms of patency using the following assumptions:

- 80% historical control rate (TASC II B and C lesions) $10\% = 70\%$
- 85% PQ Bypass Stent Graft estimated rate

The alternative hypothesis is to be one of superiority against the performance goal of 70%. As such using as historical control rate of 80% and a delta of 10%, the null and alternative hypotheses of the primary performance endpoint can be written as:

$$H_0: \pi_{PQB} \text{ performance} \leq \pi_{PG} \text{ performance}$$

$$H_A: \pi_{PQB} \text{ performance} > \pi_{PG} \text{ performance}$$

where,

$$\pi_{PG} \text{ performance} = 80\% \text{ historical control rate} - 10\% \text{ Delta} = 70\%$$

$$\pi_{PQB} \text{ performance} = \text{PQB Systems success rate}$$

The hypotheses for the primary performance endpoint can be rewritten as:

$$H_0: \pi_{PQB_performance} \leq 70\%$$

$$H_A: \pi_{PQB_performance} > 70\%$$

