To achieve 80% power using a one sided alpha of 0.05, with a clinically acceptable delta of 10%, a sample size is 50 subjects would be needed to reject the null hypothesis. The required sample size was calculating assuming a true performance rate for PQ Bypass of 85%, using the exact method (ref: Chow S.C. 2003 Sample Size Calculations in Clinical Research.), implemented using the PASS 12 software.

Table 23 : Superiority with PQ Bypass Performance of 85%

PG	PQ Bypass			
	80%	85%	90%	95%
70%	119	50	26	15
75%	441	103	42	21
80%	-	368	83	32
85%	-	-	283	60

However, due to noise in the literature, the fact that the true performance of the PQ Bypass Stent Graft is unknown at this time, and potential loss to follow up, a larger sample size is required for the Study in order to ensure 50 evaluable subjects taking into account the above assumptions. The lower the true performance rate of the PQ Bypass Stent Graft, the greater the sample size needed to reject the null hypothesis and maintain 80% power. Therefore, up to 65 subjects may be enrolled.

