16.4 Ethics Committee (EC) and Competent Authority (CA) Approval

The trial will only be started in a center after written approval of the protocol and Patient Informed Consent has been obtained from the appropriate Ethics Committee. Any amendment to the final protocol and informed consent should be submitted to the Ethics Committee.

Regulatory approvals must be obtained prior to enrolment of the first patient. The Sponsor will arrange EC and CA approvals for the study. The Sponsor or its designated CRO (HealthLink) will require a copy of any EC and CA correspondence, as well as the final approval letter from the EC and CA, where applicable.

No changes in the Clinical Investigation procedures will be effected without mutual agreement of the Principal Investigator and the Sponsor. The agreement of the changes must be documented by signing the corresponding Clinical Investigation Plan amendments.

All changes require notification to the EC/IRB and the CA (when appropriate), or approval where requested by local regulations. Substantial changes may require approval from the EC/IRB and the CA prior to implementation.

Substantial changes are changes which could:

- have an effect on the safety of the clinical investigation participants,

May not be reproduced without written permission from PQ Bypass, Inc.

- influence the interpretation of the documents on which the conduct of the clinical investigation is based, or
- influence the other requirements assessed by the ethics committee.

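### Section 11.1 sets out to show superiority to an 80% historical control, but its only test is against 70%, so meeting the endpoint cannot support that claim.

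*Combined protocol and SAP*

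**What the plan says.** Section 11.1 takes an 80% historical control rate for TASC II B and C lesions from a literature review. It says that a 10% delta and a one-sided alpha of 0.05 "were set to demonstrate superiority of the PQ Bypass Stent Graft relative to the historical control in terms of patency". The planning value for the device is given as "85% PQ Bypass Stent Graft estimated rate".

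The section then subtracts the delta from the control rate, calls the result (70%) the performance goal, and writes the null as patency at or below 70% and the alternative as patency above 70%. In words: "The alternative hypothesis is to be one of superiority against the performance goal of 70" per cent. The sample-size paragraph describes the subtraction as made "with a clinically acceptable delta of 10" per cent.

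Sections 11.1 and 11.3 give the same decision rule, based on the one-sided 95% Wilson lower limit: "If the lower limit exceeds the performance goal rate of 70% the null hypothesis will be rejected and the endpoint will be met". Section 11.1 plans 60 evaluable subjects, with up to 65 enrolled. No test against 80% appears anywhere, and the other endpoints are summarised by estimates, confidence bounds and survival curves.

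**The concern.** Section 11.1 gives two comparators for one test: the historical control (80%) and the performance goal (70%). A bar obtained by subtracting a margin from the control lies below the control. Clearing it shows that patency is above 70%, that is, less than 10 points below the 80% rate. It does not show that patency is above 80%.

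This is the trial's only hypothesis test, in a pre-market study. If the sentence stands, a report could cite the plan accurately and still describe as superior to the historical control a device that is no better than it, or somewhat worse.

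**Working it through.** **Inputs (Section 11.1 and Table 23).** Control rate 80%; delta 10 points; tested value 70%; planning rate 85%; one-sided alpha 0.05; power 80%; stated sample size 50; planned evaluable 60; maximum enrolled 65.

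**Step 1: the plan's own figure.** The one-sample score formula is

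n = [ (z₀.₉₅ √(p₀(1−p₀)) + z₀.₈₀ √(p₁(1−p₁))) / (p₁−p₀) ]², with z₀.₉₅ = 1.645 and z₀.₈₀ = 0.842.

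- p₀ = 0.70, p₁ = 0.85: [(0.7538 + 0.3005)/0.15]² = 49.4, rounded up to **50**. This matches the plan.
- p₀ = 0.80, p₁ = 0.85: [(0.6579 + 0.3005)/0.05]² = 367.5, rounded up to **368**. This matches the Table 23 cell for a goal of 80%.

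An exact binomial search gives 49 and 365. The arithmetic is therefore right for the 70% goal, and the sample size was not set for a test against 80%.

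**Step 2: what meets the endpoint with 60 evaluable.** With p = x/n and z = 1.645, the Wilson lower limit is

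L = [ p + z²/(2n) − z √(p(1−p)/n + z²/(4n²)) ] / (1 + z²/n).

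| Patent grafts | Observed | Lower limit | Above 70%? | Above 80%? |
|---|---|---|---|---|
| 47/60 | 78.3% | 68.5% | no | no |
| 48/60 | 80.0% | 70.3% | yes | no |
| 51/60 | 85.0% | 75.9% | yes | no |
| 53/60 | 88.3% | 79.8% | yes | no |
| 54/60 | 90.0% | 81.8% | yes | yes |

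The endpoint is met from 48/60, an observed rate equal to the historical control. A lower limit above 80% needs 54/60. Every result from 48/60 to 53/60 meets the endpoint without supporting superiority to 80%.

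**Step 3: how often this happens (exact binomial, n = 60).**

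- Endpoint met, P(X ≥ 48): 0.232 at a true 75%, 0.576 at 80%, 0.894 at 85%.
- Lower limit above 80%, P(X ≥ 54): 0.185 at a true 85%.
- Endpoint met but lower limit not above 80%, P(48 ≤ X ≤ 53) at a true 85%: 0.894 − 0.185 = 0.709. As a share of all successes: 0.709/0.894 = 79%.

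**Step 4: sensitivity to the evaluable number.** For n from 50 to 65:

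- The lowest passing observed rate runs from 79.7% (51/64) to 82.4% (42/51).
- The chance of meeting the endpoint is 42–60% at a true 80% and 15–24% at a true 75%.
- The chance of a lower limit above 80% at a true 85% is 16–29%.

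**The case against.** The strongest reply is that the sentence is a loosely worded lead-in to the derivation of the 70% goal. The assumptions follow it directly, the 80% minus 10% subtraction is written out, the alternative is then stated as superiority to the performance goal, and the decision rule appears twice with 70%. Table 23 is also indexed by performance goal. No statistician would run the wrong test from this plan, no passage commits the sponsor to claiming superiority to 80%, and the harm depends on a later misdescription. On the figures, 58% and 23% are ordinary power values at alternatives above a 70% null and not error rates of the specified test. The passing observed rate is close to 80% or above at every plausible sample size.

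Much of this stands. The test is openly specified, which makes this a fault in the stated conclusion and not in the analysis. But the surrounding text only shows which sentence is wrong. It does not remove the sentence, which says what the design was meant to demonstrate. The figures measure how far that statement is from what the test can deliver, and they are not offered as a fault in the 70% test.

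A further point is that Section 11.1 also expects patency to be superior to a historical control rate. That is an expectation and not a conclusion from a test. It can remain once the permitted claim is limited explicitly.

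**Conclusion.** The concern holds. As written, Section 11.1 gives the design a property it does not have. Meeting the endpoint supports patency above 70% and nothing stronger about the 80% control.

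With 60 evaluable subjects, a device equal to the control succeeds 58% of the time and one five points worse succeeds 23% of the time. Observing exactly the planned 85% would still not show superiority to 80%. These figures rest on the plan's Wilson rule, independent binary outcomes and 60 evaluable subjects; across 50 to 65 subjects the conclusion does not change. The 80% is taken as the plan states it, as a fixed rate.

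This should be fixed. It concerns what the trial's sole hypothesis test is allowed to conclude. The hypotheses, threshold and sample size agree with one another and need no change.

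**What to change.** In Section 11.1, reword the end of the sentence quoted above so that delta and alpha are set *to demonstrate that 12-month patency exceeds a performance goal of 70% (80% literature rate minus a 10-point margin)*. Then add: *Meeting this endpoint does not support a claim of superiority to the 80% historical control rate.*

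The hypotheses, the 70% threshold, the Wilson test and the sample size stay as they are. The test remains one of superiority to the performance goal, so the design need not be relabelled as non-inferiority.

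The cost is one reworded and one added sentence, with no extra subjects, data or analyses, and a less favourable permitted claim. Section 16.4 applies: "All changes require notification to the EC/IRB and the CA (when appropriate), or approval where requested by local regulations". The change should be in place before the 12-month database snapshot described in Section 14.2.

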11.2 Primary Safety Endpoint Reporting

The primary safety endpoint is the rate of Major Adverse Events (MAEs) at 30 days. The number and percent of subjects that experience at least one MAE through 30 days post procedure will be reported along with the upper one sided 95% confidence limit. In addition the number and percentage of subjects reporting MAEs and MAVEs will be presented using descriptive statistics at various time intervals, combined and by type of event. The confidence intervals will be calculated using the Wilson method.

11.3 Primary Performance Endpoint Reporting:

The primary performance hypothesis will be tested by calculating the one sided 95% lower confidence limit for the rate of successful performance using the Wilson Method. If the lower limit exceeds the performance goal rate of 70% the null hypothesis will be rejected and the endpoint will be met. In addition to hypothesis testing, descriptive statistics of the primary performance endpoint will include the total number and percentage of patent PQB grafts.

11.4 Secondary Endpoint Analysis:

The secondary endpoint of primary assisted and secondary patency will be summarized using Kaplan Meier survival analysis. Life tables will be created and a Kaplan Meier survival curve will be presented.

The secondary endpoints inclusive of Procedural Success, Clinical Success and Technical Success will be summarized by providing point estimates, number of subjects, and 95% confidence bounds calculated using the Score approximation.

11.5 Demographic, procedural and safety data:

Demographic and baseline clinical and disease characteristics will be summarized in tables. For continuous variables the summary will include number, mean, and standard deviation and 95% confidence intervals. Summaries for categorical variables will include the number and percent of subjects in each category.

11.6 Imputation for Missing Data

Imputations for missing data in (e.g. withdrawn subjects, loss to follow up, missing data) will not be performed. Analyses will be performed with all available data only.

12.0**ADVERSE EVENTS**

The occurrence of Adverse Events will be monitored during this study. All Adverse Events will be recorded on the Adverse Event Form at onset and at each follow up visit until resolved. To meet the objectives of this study, the following definitions will apply. (Definitions reference ISO 14155:2011 01). Potential adverse events associated with use of the SGS include, but are not limited to the following:

 • Access site hemorrhage or hematoma • Access site pain/infection • Acute vessel closure • Aneurysm or pseudoaneurysm formation • Arteriovenous (AV) fistula • Death • Device failure • Embolism • Fever/pain in absence of infection • Infection 	
 • Inflammation • Malposition • Myocardial infarction • Radiation injury • Renal insufficiency/failure due to excessive contrast load • Sepsis • Shock • Side branch occlusion • Stenosis or Occlusion • Thrombosis • Vessel dissection, perforation or wall trauma
--	--

12.1 Adverse Event (AE)

Adverse Event (AE): Any untoward medical occurrence, unintended disease or injury or any untoward clinical signs (including an abnormal laboratory finding) in subjects, users or other persons whether or not related to the medical device. This includes events related to the device or events related to the procedures involved.

Adverse Device Effect: An adverse event related to the use of a medical device, including adverse events resulting from insufficient or inadequate Instructions for Use, deployment, implantation, installation or operation, or any malfunction of the medical device or any event resulting from user error or intentional misuse of the medical device.

The Investigator is responsible for assessing the severity of the AE, the causal relationship between any events and the clinical study procedure, activities or device. Additionally, the Investigator is responsible for providing appropriate treatment for the event and for adequately following the event until resolution. The following categories of adverse event severity are to be used:

- Mild: Awareness of a sign or symptom that does not interfere with the subject's usual activity or is transient, resolved without treatment and with no clinical sequelae.
- Moderate: Interferes with the subject's usual activity
- Serious: Any fatal or immediately life threatening clinical experience that requires a subject to be hospitalized, or hospitalization is unduly prolonged because of potential disability or danger to life or because an intervention

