12.2 Serious Adverse Event (SAE)

Serious Adverse Event (SAE): A serious adverse event is any problem or unwanted event encountered in a clinical trial or a performance evaluation that has led, could have led, or could lead directly or indirectly to death or to a serious deterioration in the health of a subject or user or any other person, without regard to whether the event was caused by a medical product. (§ 2 no. 5 MPSV). The following events (including laboratory results and outcome events) will be considered to be SAEs and must immediately (within 24 hours) be reported to the study Sponsor by telephone, fax and/or email. These events must be reported whether or not the Investigator believes they are related to study procedures, activities or device:

- Death
- Serious deterioration in the health of the subject, that either resulted in a life threatening illness or injury, or a permanent impairment of a body structure or a body function, or in patient or prolonged hospitalization, medical or surgical intervention to prevent life threatening illness or injury or permanent impairment to a body structure or a body function.
- Malignant Tumor (Austrian Medical Device Act, § 3 Abs.16 MPG as amended)

Serious Adverse Device Effect: An adverse device effect that has resulted in any of the consequences of a Serious Adverse Event.

Note: Planned hospitalization for a pre existing condition, a condition unrelated to the treatment or a procedure required by this study, that is without serious deterioration in health, is not considered a serious adverse event.

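### Section 12.1 makes Serious the top adverse event severity grade, with criteria narrower than the SAE definition in section 12.2 and no separate Severe level

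*Combined protocol and SAP*

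**What the plan says.** Section 12.1 makes the investigator responsible for assessing severity and prescribes the scale: "The following categories of adverse event severity are to be used". It has three levels.

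- The lowest is "Mild: Awareness of a sign or symptom that does not interfere with the subject's usual activity or is transient, resolved without treatment", with no clinical sequelae.
- The middle level reads in full "Moderate: Interferes with the subject's usual activity".
- The top level begins "Serious: Any fatal or immediately life threatening clinical experience that requires a subject to be hospitalized" and continues "or hospitalization is unduly prolonged because of potential disability or danger to life or because an intervention", where the available text stops.

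Section 12.2 defines an SAE for reporting purposes. Its general definition covers any event that "has led, could have led, or could lead directly or indirectly to death or to a serious deterioration in the health of a subject". Its list then names death, and serious deterioration that results in life-threatening illness, in permanent impairment, or in "in patient or prolonged hospitalization, medical or surgical intervention to prevent life threatening illness or injury or permanent impairment". A further entry is "Malignant Tumor (Austrian Medical Device Act". Events on that list go to the sponsor within 24 hours. The SAE entry in section 19 agrees in substance with the general definition in 12.2.

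Severity is used in two other places. Section 12.4 makes it an item of the adverse event report. Section 12.3 makes it one of the features that decide whether a serious device effect is unanticipated.

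**The concern.** Severity describes how intense an event is. Seriousness describes its outcome and drives reporting. Section 12.1 puts the second term at the top of a scale for the first, and section 12.2 then defines the same word by different criteria. Nothing in the protocol says that the two uses are separate or which one prevails.

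Two things follow. Some events that are SAEs under 12.2 receive the same grade as an event that merely limits activity. And because the scale goes from interference with activity straight to a test of life-threat and hospital stay, it cannot separate a slight limitation from an incapacitating event that is not an SAE. At stake are the meaning of the severity field and the clarity of the instruction to sites.

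**Working it through.** The plan gives no figure on this point and no arithmetic applies. The check is to read the whole Serious entry in 12.1 against 12.2 and to classify test cases under each.

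**Reading the top grade.** It has two visible limbs. Limb 1 needs a fatal or immediately life-threatening event that also requires admission. Limb 2 is an unduly prolonged stay because of potential disability, danger to life or an intervention. One could parse limb 2 as still governed by the life-threat condition, but the mention of potential disability fits that poorly, so limb 2 is taken here as a separate route. It breaks off after the word intervention. That may be a loss in text extraction, so the missing words are not counted against the plan and the exact scope of the limb is left open.

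**Reading 12.2.** Admission counts when it results from serious deterioration in health. A planned admission for a pre-existing condition, without such deterioration, is expressly not an SAE. There is no added life-threat test for admission.

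| Test case | Section 12.2 | Grade under 12.1 |
|---|---|---|
| New admission for serious, not life-threatening deterioration | SAE | Fails both limbs; at most Moderate |
| Permanent impairment, no admission | SAE | Fails both limbs; at most Moderate |
| Malignant tumour, no immediate threat to life, no prolonged stay | SAE | Fails both limbs; at most Moderate |
| Event that could have led to serious deterioration but did not | SAE (general definition) | Fails both limbs; at most Moderate |
| Stay unduly prolonged for potential disability or an intervention, not life-threatening | SAE | Can be Serious through limb 2 |
| Incapacitating event that meets no SAE criterion | Not an SAE | Moderate, which has no upper bound |

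The first four rows show that the grade is narrower than the SAE definition. The fifth shows that the mismatch does not extend to every non-life-threatening hospital event. The sixth shows that a severe non-serious event can be graded, but only together with much milder ones.

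**Where the grade has an effect.** It fills the severity item required by 12.4. It is the only severity scale that the protocol offers for the criterion in 12.3, although 12.3 does not cite it. It does not enter the primary safety endpoint or the major adverse vascular event endpoint, which have their own definitions in section 5.2. Section 11 plans no table by severity.

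**The case against.** The strongest reply is that this is a labelling fault whose consequences are already contained. Much of that stands.

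- **Reporting.** The 24-hour trigger is the list in 12.2, which never refers to the 12.1 grade, and 12.6 repeats the rule. Section 12.4 also sends possible device- or procedure-related events to the sponsor within 24 hours, whatever their grade. A reader might infer that sites will fail to start the SAE route. The documents do not support that. At most a site may confuse the two uses of the word, chiefly for events it judges unrelated.
- **Adjudication.** The Protocol Summary has an independent committee or medical reviewer adjudicate safety endpoints, SAEs and device-related events.
- **Analysis.** A reader might infer that severity tables will show re-interventions as Moderate and so understate the safety burden. No such table is planned. Target lesion revascularisation counts in the primary safety endpoint, and target lesion and target vessel revascularisation are endpoints in their own right, all regardless of grade.
- **Forms.** The case report form is not in the documents, so nothing shows that it lacks a separate seriousness field.
- **Granularity.** Since Moderate has no ceiling, no event is left without a grade.

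What this reply does not remove is the mismatch itself. The scale is mandatory, its result is a required report item, and its top level sorts events by criteria that neither measure severity nor match the protocol's own definition of serious.

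**Conclusion.** The point holds as a definitional defect with limited reach. The top severity grade in 12.1 differs from, and is narrower than, the SAE definition in 12.2 and section 19, and the scale has no Severe level. It affects the severity item in adverse event reports, the severity criterion for unanticipated effects, and the clarity of SAE classification at sites. No primary endpoint, sample size or planned table changes.

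Two further inferences should be resisted. The first is that every non-life-threatening hospitalised event is graded at most Moderate: the prolonged-stay limb contradicts this.

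The second is a count borrowed from STP 115. Table 8 in section 2.3 reports 6 of 59 subjects with a major adverse event at 6 months, all target vessel revascularisations. That is 6/59 = 10.2%, and 0.102 × 60 = 6.1, so one might say that about 6 of 60 subjects here would be classified differently. The documents do not say how many of those six were admitted or how any event was graded. STP 115 was a percutaneous bypass in lesions averaging 28.6 cm, 93.3% of them TASC D, whereas this study treats 8–18 cm TASC B and C lesions. The number affected cannot be estimated.

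The conclusion rests on the literal, visible wording of 12.1. If the missing end of the Serious entry widens it, some of the test cases could move.

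**What to change.** In section 12.1:

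1. Replace the third grade with a true severity level, for example Severe: prevents the subject's usual activity.
2. Remove the fatal, life-threatening and hospitalisation wording from the scale.
3. State that seriousness is determined separately, only by the definition in 12.2, whatever the severity grade.

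The amendment should not say that 12.2 alone governs 24-hour reporting. Sections 12.3, 12.4 and 12.5 also require it for unanticipated device effects, possible device- or procedure-related events and device malfunctions, and those rules should stay unchanged.

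The cost is one definition change and possibly one field on the adverse event form. No assessment or visit is added.
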